## 6 STUDY PERIODS, TREATMENT REGIMENS AND POPULATIONS FOR ANALYSES

### 6.1 Study Periods

See Core Safety SAP.

### 6.2 Treatment Regimens

The treatment group “**as randomized**” will be retrieved from the IVRS system

- Arm A: Experimental Arm (monotherapy) nivolumab
- Arm B: Experimental Arm (combination) nivolumab + ipilimumab
- Arm C: Placebo Arm (placebo for both nivolumab and ipilimumab)

The treatment group “**as treated**” will be the same as the arm randomized by IVRS. However, if a subject received the incorrect drug for **the entire period** of treatment, the subject’s treatment group will be defined as the incorrect drug the subject actually received.

### 6.3 Populations for Analyses

- **Global study population:** all subjects enrolled during the global accrual window (from first patient first consent date to last patient outside of China’s consent date). Any patient from China enrolled during the global accrual window will be included.
- **All Enrolled Subjects:** All subjects who signed an informed consent form and are registered into IVRS during the global enrollment period
- **All Randomized Subjects:** All enrolled subjects from global study population who were randomized to any treatment group.
- **All Treated Subjects:** All randomized subjects from global study population who received at least one dose of any study medication.

- All Randomized subjects with at least one lesion at baseline : All randomized subjects from global study population with at least one lesion (target or non target) at baseline scan
- **PK Subjects:** All randomized subjects from global study population with available serum time-concentration data.
- **Immunogenicity Subjects:** All randomized subjects from global study population with available Anti Drug Antibody data.
- **Tumor Mutation Burden (TMB) evaluable Subjects:** All randomized subjects from global study population with baseline evaluable TMB.
- **China Cohort:** Subjects enrolled from China Mainland

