5 STUDY ASSESSMENTS AND PROCEDURES

5.1 Flow Chart/Time and Events Schedule

Table 5.1-1: Screening Procedural Outline (CA209451)

Procedure	Screening	Notes
Eligibility Assessments		
Informed Consent	X	Informed Consent may be obtained at any time, provided it is prior to conduct of any study-related procedures. Note that SAEs are collected from the date of consent.
Inclusion/Exclusion Criteria	X	All inclusion/exclusion criteria should be assessed at screening and confirmed prior to randomization
Medical History	X	
Prior Systemic Therapy	X	
Safety Assessments		
Physical Examination	X	
Physical Measurements	X	Include Height, Weight, and ECOG performance Status. Within 14 days prior to randomization
Vital Signs and Oxygen saturation	X	Temperature, BP, HR, and O2 saturation at rest by pulse oximetry. Obtain vital signs at the screening visit and within 72 hours prior to randomization.
Assessment of Signs and Symptoms	X	Within 14 days prior to randomization
Concomitant Medication Collection	X	Within 14 days prior to randomization
Laboratory Tests	X	CBC with differential, Chemistry panel including LDH, AST, ALT, ALP, T.Bili, BUN or serum urea level, uric acid, creatinine, Ca, Mg, Na, K, Cl, P, glucose, bicarbonates (optional), albumin, amylase or lipase, TSH (reflex to free T3, free T4 for abnormal TSH result), hepatitis B surface antigen (HBV sAg), and hepatitis C antibody (HCV Ab) within 14 days prior to randomization. Screening labs done within 72 hours prior to first dose can also be used for on treatment lab purposes at Day 1 dosing.
ECG	X	Within 28 days prior to randomization
Pregnancy Test	X	Performed within 24 hours prior to first dose for WOCBP only (serum or urine - local/site)

Table 5.1-1: Screening Procedural Outline (CA209451)

Procedure	Screening	Notes
Efficacy/Biomarker Assessments		
Radiographic Tumor Assessment	X	CT/ Chest, CT/MRI Abdomen, Pelvis, and any other known sites of disease; MRI/CT Brain (refer to section 5.4 for detail on cases where CT of the Brain is acceptable) Within 21 days prior to randomization. Additional sites of known or suspected disease (including CNS) should be imaged at the screening visit and at subsequent on-study assessments.
Collection of tumor tissue for biomarker evaluation	X	See Section 3.3.1 , Inclusion 2f
IVRS/Clinical Drug Supplies		
Phone calls to IVRS		Phone calls must be made to IVRS as follows: Screening phone call to IVRS: For subject number assignment at the time informed consent is obtained.

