8 STATISTICAL CONSIDERATIONS

8.1 Sample Size Determination

Per original protocol, approximately 810 subjects were to be randomized to the three treatment arms in a 1:1:1 ratio.

The primary objective is to compare Overall Survival (OS) of nivolumab in combination with ipilimumab versus placebo. The analysis of primary endpoint of OS will be conducted when at least 386 deaths have been observed pooled across the two treatment groups. Using accrual and treatment effect assumptions described below, it is expected that 208 events will be observed in placebo and 178 in nivolumab in combination with ipilimumab treatment groups. With 386 events available for comparison of OS in nivolumab in combination with ipilimumab vs placebo groups, power of the log-rank test is approximately 90% to detect a hazard ratio (HR) of 0.72 with a type I error of 0.05 (two-sided). The critical hazard ratio for determining whether nivolumab in combination with ipilimumab is superior to placebo is 0.82.

Power calculations were performed using EAST® Software (version 6.4.1). Results were generated by 10000 simulations. Model assumptions were as follows:

Survival function for placebo arm was modeled using a four hazard pieces: OS rates at 3, 9, 18 and 26 months were assumed to be 90%, 47%, 15% and 9%, respectively, based on published survival curve for placebo maintenance in Extensive-Stage SCLC, adjusted for induction phase³⁶. Median OS for placebo was 8.8 months.

For nivolumab in combination with ipilimumab, a delayed effect versus placebo with a hazard ratio (HR) of 1 for the first 3 months³⁷ and an HR of 0.68 thereafter was assumed, resulting into overall HR (experim vs placebo) of 0.72 at time of the OS analysis. Median OS for the experimental arm was 11.0 months.

Accrual information used in the simulations had the same pattern as the actual data at time of the protocol amendment (832 subjects were accrued in 28 months and randomized to the three treatment groups). A 5% probability of dropout by month 6 was taken into account. Given the observed accrual and dropout and survival assumptions it is expected that the duration of the study from start of randomization to final analysis will be approximately 35 months (28 months of accrual + 7 months of minimum follow-up, providing an average follow up of 9 months).

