This study includes a sub-study to allow enrollment of patients from China (site-specific protocol amendment 12). Data from these additional subjects will be reported separately. Subjects from China randomized on or before end of global study accrual will be included in the population used for the primary analysis clinical study report. The required number of deaths for the primary OS analysis is based on the global study population.

The independent Data Monitoring Committee (DMC) will have access to periodic interim safety and efficacy reports to allow for a risk/benefit assessment.

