8.2 Populations for Analyses - Data set descriptions

- Global study population: all subjects enrolled during the global accrual window (from first patient first consent date to last patient outside of China's consent date). Any patient from China enrolled during the global accrual window will be included
- All Enrolled Subjects: All subjects who signed an informed consent form and were registered into the IVRS
- All Randomized Subjects: All subjects who were randomized to any treatment group
- All Treated Subjects: All subjects who received at least one dose of any study medication
- PK Subjects: All randomized subjects with available serum time-concentration data
- Immunogenicity Subjects: All randomized subjects with available ADA data
- Biomarker Subjects: All randomized subjects with available biomarker data

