The secondary endpoints of OS in nivolumab vs placebo and PFS in experimental treatments vs placebo will be tested hierarchically (see [Section 7.5.3](#)). Assuming 386 events are also available for comparison of OS in nivolumab vs placebo, power of the log-rank test is approximately 90% to detect a hazard ratio (HR) of 0.72 with a type I error of 0.05 (two-sided).

For PFS analyses comparing nivolumab or nivolumab in combination with ipilimumab vs placebo in all randomized subjects, 525 PFS events are projected to be observed at the time of

the OS analysis, which provides approximately 93% power to the log-rank test to detect an overall HR of 0.74 with a Type I error of 0.05 (two-sided). Piecewise exponential distributions were used to model PFS. The following assumptions were made: for the placebo group, a median PFS of 2 months and PFS rate at 12 months of 5% were assumed. Both experimental arms were assumed to have median PFS of 2 months (similar to placebo), with PFS rate at 12 months of 15%.

This study includes a sub-study to allow enrollment of patients from China (site-specific protocol Amendment 12). Data from these additional subjects will be reported separately. Subjects from China randomized on or before end of global study accrual will be included in the population used for the primary analysis clinical study report. The required number of deaths for the primary OS analysis is based on the global study population.

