## 7 STATISTICAL ANALYSES

Primary population of analysis is the global study population. Demography, baseline characteristics, efficacy and safety will also be reported for the China cohort separately, analyses will be descriptive.

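### Do the consent-date and randomization-date wordings for China subjects leave the primary OS population undefined?

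*SAP*

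**What the plan says.** The formal definition is in SAP 6.3. The global study population is "all subjects enrolled during the global accrual window (from first patient first consent date to last patient outside of" China, and that patient's consent date closes the window. Protocol 8.2 uses the same window and, like SAP 6.3, adds: "Any patient from China enrolled during the global accrual window will be included". In both documents a subject is enrolled once consent is signed and the subject is registered in IVRS. Randomization comes later.

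The sample-size sections, SAP 5 and Protocol 8.1, put it differently: "Subjects from China randomized on or before end of global study accrual will be included in the population used for the primary analysis" report. Neither section says on what date global accrual ends. The sentence that follows in both is "The required number of deaths for the primary OS analysis is based on the global study population". SAP 7 then states: "Primary population of analysis is the global study population".

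SAP 6.3 builds its randomized and treated sets from the global study population. The protocol's version has no such limit: "All Randomized Subjects: All subjects who were randomized to any treatment group". SAP 2.1 expects about 70 additional subjects from China, and SAP 7 reports the China cohort descriptively.

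**The concern.** One wording turns on consent and the other on randomization, and the two dates differ for each subject. Protocol 8.1 also speaks of accrual in terms of randomization ("832 subjects were accrued in 28 months and randomized to the three treatment groups"), whereas Protocol 8.2 bounds its accrual window by consent. Because recruitment in China was expected to run past the global close, there is a real boundary, and some China subjects may fall on different sides of it under the two wordings.

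At stake would be the membership of the only confirmatory OS test, which also opens the testing hierarchy in SAP 7.5.3, and the set of deaths counted toward 386. Both wordings occur in both documents, so letting the SAP override the protocol would not choose between them. Consent timing also looks loose. Protocol Table 5.1-1 says "Informed Consent may be obtained at any time, provided it is prior to conduct of any study-related procedures", and a subject who re-enrolls is consented a second time.

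**Working it through.** **1. The plan's own figures.** Inputs from Protocol 8.1 and SAP 5: 386 deaths, HR 0.72, two-sided alpha 0.05, 1:1 for the primary comparison.

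- Critical HR = exp(−2 × 1.96/√386) = exp(−0.1995) = 0.819. The plan states 0.82.
- Power = Φ(0.3285 × √386/2 − 1.96) = Φ(1.267) = 89.7%. The plan states about 90%. This is a proportional-hazards approximation; the plan simulated a delayed effect.

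**2. Where the wordings disagree.** Let C be the last consent date outside China and R the last randomization date outside China. A China subject has consent date c and randomization date r, with c no later than r. The window admits the subject if c ≤ C. The sample-size sentence names the subject if r ≤ E, where E is the undated end of accrual.

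- If E = C, then r ≤ C forces c ≤ C. Everyone named by the sentence is already in the window. The sentence says who is included and excludes nobody, so a subject with c ≤ C < r is in by the definition and merely unmentioned by the sentence.
- If E = R, a subject with c > C and r ≤ R is named by the sentence but lies outside the window. That is a true conflict. A subject with c ≤ C and r > R conflicts only if the sentence is read as also excluding.

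**3. Which wording governs.** The required deaths (Protocol 8.1, SAP 5), the primary population (SAP 7) and the SAP's randomized set (SAP 6.3) all use the term global study population. That term is defined only in the two sections on analysis populations, and identically in both. The chain from definition to death count to log-rank set is complete without the sample-size sentence.

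**4. Which consent counts.** Protocol 4.4 requires the consent date for IVRS enrollment. Under Protocol 3.1.1.1 a re-enrolled subject is re-consented and receives a new number, and the earlier record was never randomized. The consent belonging to the randomized number is the natural one to use.

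**5. Scale.** The documents give neither a China accrual rate nor a consent-to-randomization interval. Assume 2 to 10 China randomizations a month over three arms (70 subjects would take 35 to 7 months) and a mismatch of 14 to 42 days.

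- Low: 2 × 14/30.4375 = 0.9 subjects; × 2/3 = 0.6 in the two primary arms.
- High: 10 × 42/30.4375 = 13.8 subjects; × 2/3 = 9.2 in the two primary arms.
- Deaths by 7 months, the planned minimum follow-up, with a constant hazard between the assumed placebo rates of 90% at 3 months and 47% at 9 months: the hazard is ln(0.90/0.47)/6 = 0.1083 per month. Placebo: 1 − 0.90 × exp(−4 × 0.1083) = 41.6%. Combination, with HR 0.68 after month 3: 1 − 0.90 × exp(−0.68 × 4 × 0.1083) = 33.0%. The mean is 37.3%.
- Deaths in question: 0.6 × 0.373 = 0.2 up to 9.2 × 0.373 = 3.4, which is at most 3.4/386 = 0.9% of the required number.

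**6. Effect on the design.** The analysis waits for at least 386 deaths in whichever set is used. Membership changes which deaths count and, slightly, the calendar date, but not the required number. Even if the count were off by 7, twice the upper figure above, power would be 89.2% to 90.3% and the critical HR 0.818 to 0.821.

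**The case for a change.** The best case for acting is that no passage says the definition outranks the sample-size sentence. That sentence is not idle background either: it says which China subjects enter the primary analysis, and it appears in the SAP as well as the protocol. If accrual is read as ending with the last randomization outside China, the conflict is genuine. A single confirmatory test should be reproducible from the text, and settling one sentence while the sponsor is blinded costs little. In addition, Protocol 8.4.2 tests OS in all randomized subjects, and the Protocol 8.2 definition of that set would not by itself keep later China subjects out.

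The mismatch in wording stands, and so does the missing date. The consequence does not. Ordinary practice is to program from the section on analysis populations, and the death count points there. The loose protocol definition of randomized subjects is already narrowed by SAP 6.3 and SAP 7. Rewriting the definition around randomization would have a cost of its own: subjects enrolled but never randomized would drop out of the global study population, although SAP 7.2.1 and 7.3.1 report on enrolled subjects. The China sub-study also came from site-specific Amendment 12, which is not among the documents here and may date the end of global accrual.

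**Conclusion.** This is a clerical inconsistency that analysts will resolve sensibly from the formal definition, and no change to the plan follows. Consent and randomization both precede treatment, and neither cut-off depends on arm or outcome, so the randomized comparison is unbiased and its Type I error is controlled in either set. On the assumed ranges, about 0.6 to 9 subjects in the two primary arms, and some 0.2 to 3.4 deaths, could be classified differently. The 386-death requirement, the 89.7% power and the critical HR of 0.819 are the same either way.

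The conclusion rests on two things: that analysts follow the defined population, as the death-count sentence and SAP 7 direct, and that China accrual near the global close was not far above 10 a month. Harmonizing the sentence would tidy the text but would not improve any result.

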## 7 STATISTICAL ANALYSES

Primary population of analysis is the global study population. Demography, baseline characteristics, efficacy and safety will also be reported for the China cohort separately, analyses will be descriptive.

### 7.1 General Methods

Unless otherwise noted, the bulleted titles in the following subsections describe tabulations of discrete variables, by the frequency and proportion of subjects falling into each category, grouped by treatment (with total). Percentages given in these tables will be rounded and, therefore, may not always sum to 100%. Continuous variables will be summarized by treatment group (with total) using the mean, standard deviation, median, minimum and maximum values.

Time to event distribution (i.e. progression free survival, overall survival and duration of response) will be estimated using Kaplan Meier techniques.

Median survival time along with 95% CI will be constructed based on a log-log transformed CI for the survivor function  $S(t)$ . Rates at fixed timepoints (e.g. OS at 6 months) will be derived from the Kaplan Meier estimate and corresponding confidence interval will be derived based on Greenwood formula for variance derivation and on log-log transformation applied on the survivor function  $S(t)$ .

Unless otherwise specified, the stratified log-rank test will be performed to test the comparison between time to event distributions (OS and PFS). Stratification factors will be ECOG PS (0, 1), sex (male, female) and Prophylactic Cranial Irradiation (PCI) following chemotherapy (yes, no), as entered into the IVRS.

Unless otherwise specified, the stratified hazard ratio between 2 treatment groups along with CI will be obtained by fitting a stratified Cox model with the treatment group variable as unique covariate. Stratification factors will be same as above.

Confidence intervals for binomial proportions will be derived using the Clopper-Pearson method. The difference in rates between the two treatment arms along with their two-sided

95% CI will be estimated using the following Cochran-Mantel-Haenszel (CMH) method of weighting, adjusting for the stratification factors:

$$\hat{\theta} = \frac{\sum_i w_i \hat{\theta}_i}{\sum_i w_i} \sim N \left[ \theta, \frac{\sum_i w_i^2 \left[ \frac{p_{ix}(1-p_{ix})}{n_{ix}-1} + \frac{p_{iy}(1-p_{iy})}{n_{iy}-1} \right]}{\left( \sum_i w_i \right)^2} \right]$$

where  $\hat{\theta} = p_{ix} - p_{iy}$  is the rate difference of the *i*th stratum,  $w_i = \frac{n_{ix}n_{iy}}{n_{ix} + n_{iy}}$ , and  $n_{ix}$  and  $n_{iy}$  are the number of subjects randomized to treatments x and y, respectively, in the *i*th stratum.

Stratification factors will be the same as above. Associated odds-ratio will be derived.

The p-values from sensitivity analyses for efficacy endpoints are for descriptive purpose only and not adjusted for multiplicity.

## 7.2 Study Conduct

### 7.2.1 Accrual

The accrual pattern will be summarized per country, investigational site and per month for all enrolled subjects. Randomization date, first dosing date, country, investigational site will be presented in a by subject listing of accrual.

### 7.2.2 Relevant Protocol Deviation

The relevant protocol deviations will be summarized for all randomized subjects, by treatment group and overall. The following programmable deviations from inclusion and exclusion criteria will be considered as relevant protocol deviations. Non-programmable relevant eligibility and on-treatment protocol deviations, as well as significant (both programmable and non-programmable) eligibility and on-treatment protocol deviations will be reported through ClinSIGHT listings.

#### Eligibility:

- Subjects with wrong cancer diagnosis :subjects with cell type other than small cell carcinoma
- Subject with baseline ECOG PS > 1.
- Subjects who received prior treatment with anti-PD-1, anti-PD-L1, anti-PD-L2, anti-CD137, or anti-CTLA-4 antibody (including ipilimumab or any other antibody or drug specifically targeting T-cell co-stimulation or checkpoint pathways)
- Subjects who received prior treatment other than acceptable combinations, as recommended per NCCN guidelines, include cisplatin or carboplatin combined with either etoposide or irinotecan.

- Subjects who received more than 4 cycles of platinum Chemo
- Subjects with best response to first line chemotherapy not CR, PR, or SD or progressed before randomization
- Subjects who received less than 4 cycles of platinum-based first line chemotherapy and reason regimen was discontinued not due to toxicity

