3.3.1 Inclusion Criteria

1. Signed Written Informed Consent

- a) Subjects must have signed and dated an IRB/IEC approved written informed consent form in accordance with regulatory and institutional guidelines. This must be obtained before the performance of any protocol related procedures that are not part of normal subject care
- b) Subjects must be willing and able to comply with scheduled visits, treatment schedule, laboratory tests and other requirements of the study

2. Target Population

- a) Subjects with SCLC documented by histology or cytology from brushing, washing or needle aspiration of a defined lesion, but not from sputum cytology alone
- b) Subjects must have presented at initial diagnosis with extensive stage disease (defined as Stage IV (T any, N any, M1a/b) per NCCN guidelines Version 1.2015, AJCC Cancer Staging Manual, 7th Edition, 2010)
- c) Eastern Cooperative Oncology Group (ECOG) Performance Status (PS) 0 or 1 (See [Appendix 1](#))
- d) Subjects must have received 4 cycles of platinum-based first line chemotherapy and must have an ongoing response of complete response (CR), partial response (PR), or stable disease (SD) after completion of chemotherapy. Acceptable combinations, as recommended per NCCN guidelines, include cisplatin or carboplatin combined with either etoposide or irinotecan
 - i) As an exception to the above criterion, subjects receiving only 3 cycles of chemotherapy due to toxicity are eligible, if they have an ongoing PR or CR after the 3rd cycle
 - ii) Subjects who have received > 4 cycles of platinum-based first line chemotherapy are not eligible
- e) Subjects must be randomized ≤ 9 weeks (63 days), from the last dose of platinum-based first line chemotherapy. Subjects receiving PCI or Brain RT must be randomized ≤ 11 weeks (77 days) from the last dose of platinum-based first line chemotherapy
 - i) Blinded study therapy must not be administered < 3 weeks (21 days) from the last dose of platinum-based first line chemotherapy
 - ii) Blinded study therapy must not be administered < 2 weeks (14 days) from the last dose of radiotherapy

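### The SAP's programmed deviation rule for fewer than 4 chemotherapy cycles is looser than inclusion criterion 2d(i), so the relevant-deviation summary may under-count departures from that criterion

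*SAP*

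**What the plan says.** Protocol section 3.3.1, inclusion 2d, asks for 4 platinum-based cycles with an ongoing CR, PR or SD. Item 2d(i) gives the only route in with fewer: "subjects receiving only 3 cycles of chemotherapy due to toxicity are eligible, if they have an ongoing PR or CR after the 3rd cycle". Item 2d(ii) excludes more than 4 cycles. Item 2e sets the time limit: "Subjects must be randomized ≤ 9 weeks (63 days), from the last dose of platinum-based first line chemotherapy", and "Subjects receiving PCI or Brain RT must be randomized ≤ 11 weeks (77 days) from the last dose of platinum-based first line chemotherapy".

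SAP section 7.2.2 lists seven eligibility deviations to be programmed and summarized by treatment group and overall. Three concern induction chemotherapy and the response to it:

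- Too many cycles, which mirrors 2d(ii), is flagged by a bullet that needs no change.
- Response is tested whatever the cycle count: "Subjects with best response to first line chemotherapy not CR, PR, or SD or progressed before randomization".
- Too few cycles is tested together with the reason for stopping: "Subjects who received less than 4 cycles of platinum-based first line chemotherapy and reason regimen was discontinued not due to toxicity".

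None of the seven tests the 2e window. The same section sends two further groups to ClinSIGHT listings: relevant deviations that cannot be programmed, and significant deviations whether programmable or not. SAP section 7.3.4 separately tabulates number of cycles, best response to first line, reason for discontinuation, and time from last chemotherapy dose to randomization.

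**The concern.** The third bullet is the SAP's version of 2d(i), but it carries over only one of three conditions. The protocol requires exactly 3 cycles, stopping because of toxicity, and a PR or CR that is still ongoing. The SAP tests only the reason for stopping. A programmer following the SAP exactly would pass a subject who stopped for toxicity after 1 cycle, or after 3 cycles with no better than SD.

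What is at stake is the accuracy of a descriptive table. Cycles completed and response to induction are what define a maintenance population, and protocol section 3.3.2 closes by stressing that every eligibility criterion must be fully met. A reader using the deviation summary to judge adherence to 2d would see a count that can be too low. No estimate or test depends on it.

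**Working it through.** There is no stated figure to reproduce; the check compares two sets of rules.

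**Inputs.** Protocol rule from section 3.3.1, items 2d, 2d(i) and 2d(ii). SAP rule from the three bullets of section 7.2.2 described above.

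- Protocol eligible on 2d = (4 cycles and response CR, PR or SD) or (3 cycles and toxicity and response CR or PR).
- SAP flagged = (more than 4 cycles) or (response not CR, PR or SD) or (fewer than 4 cycles and reason not toxicity).

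**Enumeration.** Cycles 1 to 6, stopped for toxicity yes or no, response CR, PR, SD or PD: 6 × 2 × 4 = 48 profiles. Response is taken as both the best and the current status.

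| Cycles | Reason | Response | Profiles | Protocol 2d | SAP 7.2.2 |
|---|---|---|---|---|---|
| 1 or 2 | toxicity | CR, PR, SD | 6 | ineligible | **not flagged** |
| 1 or 2 | other | CR, PR, SD | 6 | ineligible | flagged |
| 3 | toxicity | CR, PR | 2 | eligible | not flagged |
| 3 | toxicity | SD | 1 | ineligible | **not flagged** |
| 3 | other | CR, PR, SD | 3 | ineligible | flagged |
| 4 | either | CR, PR, SD | 6 | eligible | not flagged |
| 1 to 4 | either | PD | 8 | ineligible | flagged |
| 5 or 6 | either | any | 16 | ineligible | flagged |

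The profiles sum to 48. Eligible: 2 + 6 = 8. Ineligible: 48 − 8 = 40. Flagged: 6 + 3 + 8 + 16 = 33, all ineligible. Ineligible but unflagged: 40 − 33 = 7, made up of 6 + 1. No eligible profile is flagged, so the mismatch runs one way. These are logical combinations, not frequencies.

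**With the bullet aligned to 2d(i).** The 7 profiles become flagged (33 + 7 = 40) and the 8 eligible ones stay unflagged. No mismatch remains.

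**Window in 2e.** The limits are 9 × 7 = 63 days, or 11 × 7 = 77 days with PCI or brain radiotherapy.

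| Days from last chemotherapy | No PCI or brain RT | PCI or brain RT | Category in SAP 7.3.4 | Programmed flag |
|---|---|---|---|---|
| up to 63 | within limit | within limit | 9 weeks or less | none |
| 64 to 77 | outside | within limit | > 9 weeks | none |
| 78 or more | outside | outside | > 9 weeks | none |

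The > 9 weeks category therefore mixes eligible and ineligible subjects and cannot stand in for a flag. The 11-week cut in SAP 7.3.4 does not help: it runs from last radiotherapy, not from last chemotherapy.

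**Scale.** Protocol section 8.1 gives 832 randomized subjects, so each 1% affected would be 0.01 × 832 ≈ 8 subjects over the three arms. This is a conversion only; the documents give no rate.

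**The case against.** A reader might infer that ineligible subjects will be reported as eligible. The documents do not support that. The SAP never declares an unflagged subject eligible, and section 7.2.2 gives significant eligibility deviations a second route, the ClinSIGHT listings, even when they are programmable. A 2-cycle subject or a late randomization could appear there. This part of the objection stands. It does not remove the gap, because the documents do not say whether these cases count as significant, and a listing is not the summary by treatment group.

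It can also be said that section 7.3.4 already shows the underlying variables. That holds in part: subjects with 1 or 2 cycles would be visible in the table of cycles received. But cycles, reason and response are specified as separate items, so 3 cycles, toxicity and SD would not be isolated.

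On the window, the objection is stronger. The list is the sponsor's selection of relevant deviations, not a copy of every criterion. It also leaves out other computable ones, such as the laboratory limits in protocol section 3.3.2, baseline imaging within 21 days, and the 21-day minimum between chemotherapy and study therapy. Omitting the window may be a choice. The cycle bullet is different: there the SAP set out to encode a criterion and did so incompletely.

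Two practical cautions also stand. Amendment 11 (31-Aug-2016) extended the limits from 7 to 9 weeks, and from 9 to 11 weeks with PCI, so a single 63/77-day test could apply the wrong limit to anyone randomized under an earlier version. And protocol section 3.1.1.1 counts stereotactic radiation as brain radiotherapy, while SAP 7.3.4 lists only PCI, whole brain and other, so the 77-day group may not be separable from those categories alone.

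**Conclusion.** The point holds in a limited form, as a minor matter. Followed exactly, the programmed rule for fewer than 4 cycles does not flag subjects who stopped for toxicity after 1 or 2 cycles, or after 3 cycles with only SD. If such subjects exist, the relevant-deviation summary under-counts departures from 2d(i); it cannot over-count them. The absence of the 2e window from the list is a weaker, secondary observation.

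The number affected is unknown, and no document shows an affected subject. SAP section 6.3 defines no per-protocol population and section 7.5.1 compares OS in all randomized subjects, so the OS analysis, alpha and power are unaffected. It would go too far to say that the study population is misdescribed throughout, since the ClinSIGHT listings and the section 7.3.4 tables remain. The conclusion rests on reading the SAP bullet literally and on the response being recorded as it stood after the third cycle.

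**What to change.** In SAP section 7.2.2, reword the bullet so that it flags fewer than 4 cycles unless all three conditions of inclusion 2d(i) are met: exactly 3 cycles, regimen stopped for toxicity, and PR or CR ongoing after the third cycle. Section 7.3.4 names best response; if ongoing status is not available as data, state the proxy used (for example, best response CR or PR with no progression before randomization). This introduces no new eligibility rule.

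As an optional addition, flag randomization beyond the 2e window: 63 days, or 77 days with PCI or brain radiotherapy, or the limit in the protocol version in force when the subject was randomized. Say how stereotactic brain radiotherapy is identified. The alternative is one sentence stating that ClinSIGHT captures and counts these cases.

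The cost is one reworded bullet and a short programming change, plus a second bullet or sentence if the window is added. The window flag needs somewhat more work because of the version and radiotherapy details. The only downside is that the reported deviation rate may rise slightly.
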